#### Monitoring during the study

For all participants, monitoring for TB is to be continuous throughout the study. At a minimum, each participant is to have the following documented at least every 3 months:

- Thorough history to determine any risk factors for TB infection and for TB progression, and symptoms or signs of active TB, and
- Thorough physical examination for signs of active TB, including measurement of body temperature and assessment of peripheral lymph nodes (Sections 8.2.1 and 8.2.2).

#### 8.2.9. Hepatitis B Testing and Monitoring

initial testing for HBV infection includes HBsAg and anti-HBc.

- If HBsAg is positive, the participant is excluded.
- If HBsAg is negative and anti-HBc is negative, the participant is not excluded.
- If HBsAg is negative and anti-HBc is positive, further testing for HBV DNA is required.
  - If the screening HBV DNA is positive, the participant is excluded.
  - If the screening HBV DNA is negative, the participant is not excluded. Repeat testing for HBV DNA is required at least every 3 months during the study.

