Fasting visit		X							X	Participants should not eat or drink anything except water for 12 hours before the visit.
										study intervention. See Section 8.2.8 and Appendix 7, Section 10.7.
HIV screening tests	X									
Hepatitis C Virus (HCV) screening tests	X									If HCV antibody test is positive, it must be followed by an HCV RNA test. See Section 8.2.10.
Hepatitis B Virus (HBV) screening tests	X									Includes testing for HBsAg and anti-HBc. See Section 8.2.9.
HBV DNA	X								X	Only for participants who are positive for anti-HBc at screening. See Section 8.2.9.
CCI										
C-reactive protein, high-sensitivity (hsCRP)		X							X	
Pharmacokinetic (PK) samples (predose)		X			X	X	X		X	Starting at Visit 5, for each PK sample collected, record time and date of previous dose administration.
Pharmacokinetic (PK) samples (postdose)		X		X					X	For each PK sample collected, record time and date of previous dose administration. At Visit 2 and Visit 9, collect 2 PK samples: one in the period of 0.5 to 2 hours and one in the period of 3 to 4 hours postdose. At Visit 4 collect at any time postdose. All actual sample dates and times should be recorded.
Stored samples										
Genetics sample		X								Sample can be obtained at or after the specified visit.

Study J4H-MC-FVAA	Screening		D	ouble-I	Blind T	reatme	Comments			
Visit number	1	2	3	4	5	6	7	8	9	
Weeks from randomization	≤5		1	2	4	6	8	10	12	
Visit interval tolerance (days)	≤35		±3	±3	±3	±3	±3	±3	±3	
Fasting visit		X							X	Participants should not eat or drink anything except water for 12 hours before the visit.
CCI										
Skin biopsy		X							X	Optional  Visit 2: 1 biopsy each of lesional and non- lesional skin.  Visit 9: 1 biopsy of lesional skin.  See Appendix 10, Section 10.10
Randomization and dosing										
Register visit with IWRS	X	X	X	X	X	X	X	X	X	
Randomization via IWRS		X								
Dispense study intervention to participant (for at home dosing)		X			X		X			
Observe participant administer study intervention		X		X	X		X		X	Participants will be instructed to withhold study intervention on study visit days, until after predose laboratory samples have been collected.
Participant brings study intervention			X	X	X	X	X	X	X	
Assess study intervention compliance			X	X	X	X	X	X	X	

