							(see Section 7.2).
Visit interval tolerance (days)	 	—	±3	±3	±7	±7	
Fasting visit	X						Participants should not eat or drink anything
							except water for 12 hours before the visit.
Laboratory tests and sample collecti	ons						
Hematology	X		X	X	X	X	
Clinical chemistry	X		X	X	X	X	
Estimated glomerular filtration rate	X						Will be calculated by the Lilly-designated
(eGFR)							laboratory using the CKD-EPI creatinine
							equation (2021).
Lipid panel	X						Lipid panel to be collected at ED only if ED is
							before Week 12. If a participant attends this visit
							in a nonfasting state, the sample should still be
							collected. This will not be considered a protocol
							deviation.
Urine pregnancy (local)	X			X			Urine pregnancy test will be done for all
							WOCBP. See Sections 8.2.7 and 10.4.
							Additional urine pregnancy
							testing can be performed as required during the
							study or at the investigator's discretion or if
	1						required per local regulations.
Urinalysis	X						
HBV DNA	X					X	Only for participants who are positive for
							anti-HBc at screening. See Section 8.2.9.

26

Study J4H-MC-FVAA			Post-Treatment Follow-up			up	Comments
Visit number			801	802	803**	804**	For discontinuations that occur before Visit 802, see
	ED	UV*					the activities listed for ED in this table.
Weeks from randomization	_		14 or ED	16 or ED	20 or ED	24 or ED	* For unscheduled visits (UV), additional safety
			+	+	+	+	laboratory tests and procedures should be performed
			2 weeks	4 weeks	8 weeks	12 weeks	as needed.
			after last	after last	after last	after last	** V803 and V804 will only be performed if the
			dose	dose	dose	dose	PASI score from the previous visit (V802 and V803,
							respectively) is less than the baseline PASI score
							(see Section 7.2).
Visit interval tolerance (days)			±3	±3	±7	±7	
Fasting visit	X						Participants should not eat or drink anything
							except water for 12 hours before the visit.
C-reactive protein, high-sensitivity	X						
(hsCRP)							
Pharmacokinetic (PK) samples	X						For each PK sample collected, record time and
							date of previous dose administration. Sample can
							be obtained at any time during the visit.
Stored samples							
CCI							
Dosing							
Register visit with IWRS	X		X	X	X	X	
Participant returns study intervention	X						
Assess study intervention compliance	X						

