## 4. Study Design

## 4.1. Overall Design

Study FVAA is a Phase 2, randomized, double-blind, placebo-controlled study to evaluate the efficacy and safety of LY3972406 in adults with moderate-to-severe plaque psoriasis.

The study duration will be approximately 29 weeks over 3 study periods:

- **Screening**: occurs within 35 days before the planned randomization visit (baseline; Visit 2/Week 0)
- **Double-blind treatment period**: lasts for 12 weeks from baseline
- **Post-treatment follow-up**: lasts for up to 12 weeks after last treatment visit (or last dose for ED) (Visits 801-804)

**Note:** Visits 803 and 804 will only be performed if the PASI score from the previous visit (Visits 802 and 803, respectively) is less than the baseline PASI score (see Section 7.2 for details).

See SoA (Section 1.3) for additional details about the study visits and visit specific- assessments. The study schema is presented in Section 1.2.

The study will have 2 stages.

- In Stage 1, approximately participants will be randomly assigned to receive LY3972406 CCl or placebo CCl
- Stage 2 may be initiated at the sponsor's discretion post review of the interim analysis data from Stage 1, to collect additional safety and efficacy data at the collect dose level (see Section 9.4). If Stage 2 is implemented, approximately an additional participants will be enrolled. The participants will be randomly assigned to receive either

```
LY3972406 CCl , LY3972406 CCl or placebo CCl

OR

LY3972406 CCl or placebo CCl
```

For randomization stratification factors, see Section 6.3.

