## Symptom-directed physical examination after screening

These assessments are performed based on participant status and standard of care. These examinations should also include an assessment of TB risk factors and symptoms or signs of TB, including an assessment of peripheral lymph nodes, at least every 3 months during the study (Section 8.2.8).

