# Screening period guidance

To ensure safety of study participants, laboratory values and other eligibility assessments taken at screening visit are valid for a maximum of 35 days. The following rules will be applied for active, nonrandomized participants whose participation in the study must be paused due to exceptional circumstances:

- If screening is paused for less than 35 days from screening to randomization visit: the participant will proceed to the next study visit per the usual SoA, provided that randomization visit must be conducted within 35 days from first screening.
  - The site should conduct the next visit if the participant's eligibility criteria are confirmed, and the site should document the reason for delay.

 Due to the pause in screening, sites should also reconfirm the impacted participant's consent and document this confirmation in the source documentation.

• If screening is paused for more than 35 days from screening to randomization visit: The participant must be discontinued because of screening interruption due to an exceptional circumstance. This is documented as a screen failure in the CRF. The participant can reconsent and be rescreened as a new participant. This rescreen is in addition to the one allowed by the main protocol. The screening procedures per the usual SoA should be followed, starting at screening visit to ensure participant eligibility by randomization visit.

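### In a 12-week completer, no scheduled HBV DNA result arrives while study drug is being taken, so the HBV DNA stopping rules have no routine trigger

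*Protocol*

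**What the plan says.** Protocol Section 8.2.9 admits participants who are HBsAg-negative, anti-HBc-positive and HBV DNA-negative at screening. For them it adds: "Repeat testing for HBV DNA is required at least every 3 months during the study". It names no date from which the 3 months run.

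The HBV DNA row of Section 1.3.1 is marked at Visits 1 and 9, with the comment "Only for participants who are positive for anti-HBc at screening". Section 1.3.2 adds the early discontinuation visit and Visit 804. No HBV DNA test is marked at Visits 2 to 8.

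Section 4.1 states that screening "occurs within 35 days before the planned randomization visit". Appendix 13 (Section 10.13) says that "laboratory values and other eligibility assessments taken at screening visit are valid for a maximum of 35 days".

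A detected result has consequences for dosing. Section 7.1.3 requires permanent discontinuation when HBV DNA becomes positive. Section 7.1.4 requires drug to be withheld and the test repeated when the result is positive but below quantification. Section 8.2.9 repeats both actions and adds specialist care.

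On dosing, Section 1.3.1 marks dispensing at Visits 2, 5 and 7 only. Observed dosing is marked last at Visit 9, with the instruction: "Participants will be instructed to withhold study intervention on study visit days, until after predose laboratory samples have been collected".

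**The concern.** The HBV DNA rules exist to stop or pause an investigational drug when the virus becomes detectable. That needs a result while the participant is still taking drug. The Visit 9 sample is an on-drug sample, but no drug is dispensed at that visit and dosing ends there. For a completer, its result can start specialist care but has no dosing left to stop. The participants concerned are those whom the protocol itself singles out for repeat testing.

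The missing start date adds to this. A site or monitor reading 8.2.9 cannot tell whether following the schedule satisfies the 3-month requirement when screening has been long.

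**Working it through.** **Calendar check.** Screening of 35 days is 5 weeks, and 5 + 12 + 12 = 29 weeks. This matches the approximate study duration in Section 4.1, so the visit calendar is being read as intended.

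**Inputs.** Screening lasts up to 35 days (Sections 4.1 and 10.13). In Section 1.3.1, Visit 5 is Week 4 (day 28), Visit 6 is Week 6 (day 42) and Visit 9 is Week 12 (day 84), each ±3 days. Three calendar months are 89 to 92 days; 91 is used below.

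**Step 1: scheduled results during dosing.**
- The tests marked for a 12-week completer before follow-up are Visit 1 (before dosing) and Visit 9 (last dose).
- HBV DNA tests marked at Visits 2 to 8: none.
- Scheduled results that could arrive between the first and last dose: none. This holds whichever date starts the 3-month clock.

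**Step 2: interval to the first repeat.**
- From randomization: 84 ± 3 = 81 to 87 days, within 3 months.
- From a Visit 1 draw: 35 + 84 = 119 days with full screening and Visit 9 on target, and 119 + 3 = 122 days with Visit 9 three days late. The excess over 3 months is 122 − 92 = 30 to 122 − 89 = 33 days.
- Threshold with Visit 9 on target: 91 − 84 = 7, so screening of 8 days or more gives a test-to-test gap above 91 days.

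**Step 3: effect of one added test.**

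| Added at | Visit days | Max gap from Visit 1 | Max gap to Visit 9 | Dosing days left after sample |
|---|---|---|---|---|
| Visit 5 | 25 to 31 | 35 + 31 = 66 | 87 − 25 = 62 | 81 − 31 = 50 to 87 − 25 = 62 |
| Visit 6 | 39 to 45 | 35 + 45 = 80 | 87 − 39 = 48 | 81 − 45 = 36 to 87 − 39 = 48 |

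Every gap is below 89 days. The dosing days run from the sample date. The documents give no assay turnaround, which would shorten them.

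**The case against.** The strongest reply is that the schedule already does what 8.2.9 asks. Much in the protocol supports a clock that starts at randomization:
- Section 8.2.8 separates screening from monitoring during the study, and puts its own 3-monthly rule under the latter.
- Section 8.2.2 uses the same 3-month phrase under a heading for examinations after screening.
- The next subheading in 8.2.9 speaks of enrolled participants, and Appendix 14 defines enrolling as assignment to a treatment.
- The schedule's HBV DNA rows cite 8.2.9 and place repeats at Weeks 12 and 24.

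This largely stands. A reader might infer that the schedule contradicts 8.2.9, but the documents do not support that as a finding. What remains on the other side is that Section 4.1 counts screening as one of the three study periods, that the repeat sentence sits in the bullet about a negative screening result, and that no Visit 2 sample is taken. These leave the start date open without settling it.

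It can also be said that a late result follows from any 3-month interval in a 12-week treatment period, so asking for an earlier test asks for more than 8.2.9 requires. That is right about compliance. It does not answer the observation that the stopping rules have no scheduled result to act on.

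Finally, there is a route to testing during treatment. Chemistry is drawn at every treatment visit. The comprehensive hepatic evaluation in Section 8.2.11 includes hepatitis B tests as a minimum, and Appendix 6 lists HBV DNA, subject to a reflex/confirmation footnote. Appendix 2 also allows extra tests. This is real but partial cover. The 48 to 72 hour repeat panel does not name HBV DNA. With baseline ALT and AST below 1.5x ULN, the aminotransferase trigger for the full evaluation is 5x ULN, or 2x ULN with signs or symptoms. The stopping rules, by contrast, turn on HBV DNA itself.

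**Conclusion.** The point holds as a low-cost safety improvement. For anti-HBc-positive, HBV DNA-negative participants who complete 12 weeks, no scheduled HBV DNA result can act on dosing. This needs no assumption about the start of the 3 months. It does not mean that reactivation would necessarily be missed during treatment, because liver-test-triggered and discretionary testing remain. Early discontinuers are tested at their discontinuation visit.

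The interval point is conditional. The 122 days assumes a clock from the screening test, an HBV DNA draw at Visit 1 on day −35, and a Visit 9 three days late. The documents do not say whether the HBV DNA test that follows a positive anti-HBc uses the Visit 1 draw; a later draw would shorten the gap. Screening lengths of 8 to 35 days make up 28 of the 35 permitted, and a reader might infer that most affected participants would exceed 3 months. That count is of calendar lengths, not participants. No distribution of screening times is given, and on the randomization clock none exceeds 3 months at Visit 9.

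The number of anti-HBc-positive participants is not stated and may be small. No efficacy analysis is affected.

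**What to change.** In Section 1.3.1, mark HBV DNA for anti-HBc-positive participants at Visit 5 or at Visit 6. Blood is already drawn at both. Visit 5 leaves more dosing time in which a positive result can stop drug; Visit 6 shortens the gap to Visit 9. Either meets 8.2.9 through Visit 9 on both readings.

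A test at Visit 2 would satisfy the interval (at most 35 days from Visit 1, then at most 87 to Visit 9), but it would still leave no result from a sample taken after dosing has begun and before Visit 9.

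The cost is one extra assay per affected participant and one mark in the schedule. Stating in 8.2.9 when the 3 months start would be a helpful clarification, but it is not needed once the test is added. No change to follow-up testing is needed for this point.

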## Management of enrolled participants with detectable HBV DNA during the study

If HBV DNA is detected, study intervention will be temporarily withheld or permanently discontinued, as described in Sections 7.1.4 and 7.1.3, and the participant should receive appropriate follow-up medical care from a hepatologist or other specialty physician with expertise in evaluation and management of viral hepatitis.

# 8.2.10. Hepatitis C Testing and Monitoring

As specified in the SoA (Section 1.3), initial testing for HCV infection includes testing for anti-HCV.

- If anti-HCV is positive, a test for circulating HCV RNA is required.
- If HCV RNA test is negative, the participant is not excluded.
- If HCV RNA test is positive, the participant is excluded (see Section 5.2).

Participants who have had HCV infection and have been successfully treated, defined as a sustained virologic response (HCV RNA by PCR negative for at least 24 weeks following treatment completion) are not excluded on the basis of HCV as long as HCV RNA test is negative at screening.

If HCV RNA is detected during the study, the study intervention will be discontinued, and the participant should receive appropriate follow-up medical care from a hepatologist or other specialty physician with expertise in evaluation and management of viral hepatitis (Section 7.1.3).

## **8.2.11.** Hepatic Safety Monitoring

# Close hepatic monitoring

Laboratory tests (Appendix 6, Section 10.6), including ALT, AST, ALP, TBL, direct bilirubin, GGT, and creatine kinase, should be repeated within 48 to 72 hours to confirm the abnormality and to determine if it is increasing or decreasing, if 1 or more of these conditions occur:

If a participant with baseline results of	develops the following elevations:
ALT or AST <1.5x ULN	ALT or AST ≥2x ULN
ALP <1.5x ULN	ALP ≥2x ULN
TBL <1.5x ULN	TBL ≥2x ULN (except for participants with Gilbert's syndrome)
ALT or AST ≥1.5x ULN	ALT or AST ≥2x baseline
ALP≥1.5x ULN	ALP ≥2x baseline
TBL ≥1.5x ULN	TBL ≥1.5x baseline (except for participants with Gilbert's syndrome)

If the abnormality persists or worsens, clinical and laboratory monitoring, and evaluation for possible causes of abnormal liver tests should be initiated by the investigator in consultation with the Lilly-designated medical monitor. At a minimum, this evaluation should include physical examination and a thorough medical history, including symptoms, recent illnesses (for example, heart failure, systemic infection, hypotension, or seizures), recent travel, history of concomitant

medications (including over-the-counter), herbal and dietary supplements, history of alcohol drinking and other substance abuse.

Initially, monitoring of symptoms and hepatic biochemical tests should be done at a frequency of 1 to 3 times weekly, based on the participant's clinical condition and hepatic biochemical tests. Subsequently, the frequency of monitoring may be lowered to once every 1 to 2 weeks, if the participant's clinical condition and laboratory results stabilize. Monitoring of ALT, AST, ALP, and TBL should continue until levels normalize or return to approximate baseline levels.

#### Comprehensive hepatic evaluation

A comprehensive evaluation should be performed to search for possible causes of liver injury if 1 or more of these conditions occur:

If a participant with baseline results of	develops the following elevations:	
ALT or AST <1.5x ULN	ALT or AST ≥2x ULN with hepatic signs/symptoms a , or	
	ALT or AST ≥5x ULN	
ALP <1.5x ULN	ALP ≥3x ULN	
TBL <1.5x ULN	TBL ≥2x ULN (except for participants with Gilbert's syndrome)	
ALT or AST ≥1.5x ULN	ALT or AST ≥2x baseline with hepatic signs/symptoms a , or	
	ALT or AST ≥3x baseline	
ALP ≥1.5x ULN	ALP ≥2x baseline	
TBL ≥1.5x ULN	TBL $\geq$ 2x baseline (except for participants with Gilbert's syndrome)	

<sup>a Hepatic signs/symptoms are severe fatigue, nausea, vomiting, right upper quadrant abdominal pain, fever, rash, and/or eosinophilia >5%.

At a minimum, this evaluation should include physical examination and a thorough medical history, as outlined above, as well as tests for prothrombin time INR; tests for viral hepatitis A, B, C, or E; tests for autoimmune hepatitis; and an abdominal imaging study (for example, ultrasound or CT scan).

Based on the patient's history and initial results, further testing should be considered in consultation with the Lilly-designated medical monitor, including tests for hepatitis D virus, cytomegalovirus, Epstein-Barr virus, acetaminophen levels, acetaminophen protein adducts, urine toxicology screen, Wilson's disease, blood alcohol levels, urinary ethyl glucuronide, and blood phosphatidylethanol. Based on the circumstances and the investigator's assessment of the participant's clinical condition, the investigator should consider referring the participant for a hepatologist or gastroenterologist consultation, magnetic resonance cholangiopancreatography, endoscopic retrograde cholangiopancreatography, cardiac echocardiogram, or a liver biopsy.

# 8.2.11.1. Additional Hepatic Data Collection (Hepatic Safety CRF) in Study Participants Who Have Abnormal Liver Tests During the Study

Additional hepatic safety data collection in hepatic safety CRF should be performed in study participants who meet 1 or more of the following 5 conditions:

1. Elevation of serum ALT to  $\geq 5x$  ULN on 2 or more consecutive blood tests (if baseline ALT <1.5x ULN)

• In participants with baseline ALT  $\geq$ 1.5x ULN, the threshold is ALT  $\geq$ 2x baseline on 2 or more consecutive tests

- 2. Elevated TBL to ≥2x ULN (if baseline TBL <1.5x ULN) (except for cases of known Gilbert's syndrome)
  - In participants with baseline TBL  $\geq$ 1.5x ULN, the threshold should be TBL  $\geq$ 2x baseline
- 3. Elevation of serum ALP to  $\ge 2x$  ULN on 2 or more consecutive blood tests (if baseline ALP < 1.5x ULN)
  - In participants with baseline ALP  $\geq$ 1.5x ULN, the threshold is ALP  $\geq$ 2x baseline on 2 or more consecutive blood tests
- 4. Hepatic event considered to be an SAE
- 5. Discontinuation of study intervention due to a hepatic event

Note: the interval between the 2 consecutive blood tests should be at least 2 days.

## 8.2.12. Suicidal Ideation and Behavior Risk Monitoring

# Screening for suicidal ideation or behavior

ccl , screening for suicidal ideation or behavior includes the

# Monitoring for suicidal ideation and behavior

Throughout the study, participants should be monitored appropriately and observed closely for suicidal ideation and behavior or any other unusual changes in behavior, especially at the beginning and end of the course of study intervention.

# Discontinuation of participants with signs of suicidal ideation or behavior

Participants who have signs of suicidal ideation or behavior should be considered for discontinuation of study intervention, following a risk assessment (see Section 7.1.3).

